**CENTRE**  
 FOR HEALTH AND  
 POPULATION RESEARCH

October 18, 1999

*[name]*  
 For comments please  
*send*

To : [name]  
 Chairman, Ethical Review Committee

From : [name] [name] *[name]*  
 Clinical Sciences Division

Thru: Division Director, CSD *J*

Sub : Protocol # 99-020

Thank you very much for your letter with the comments on the above protocol. Please find below the answers to the comments:

- a) We will initially study 160 women to determine the prevalence of *Helicobacter pylori* infection, low gastric acid secretion and iron deficiency anemia. For the Part 2 of the study, we will screen another 138 women. Therefore, the total number of women to be screened will be 160 + 138=298. The figure (500) as mentioned in page 9 has been corrected.
- b) The subjects will be screened for worm infestation. And those with heavily infested with *Ankylostoma duodenale* will not be included. The comment has been incorporated in page 16, section 2.4.
- c) Lactating women below 2 months of lactation will not be included. (page 16, section 2.4).
- d) The adverse events those related to Injection pentagstrin are rare. However, possible side effects have been mentioned and the appropriate measure to manage such events has been included in page. 11, section 1.1.3, paragraph #3.
- e) The placebo and the group (iii) with iron therapy alone will be provided anti-Hp therapy plus iron and Anti-hp therapy respectively after completion of the study. The comments have been included in page 14, section 2.1, last paragraph.
- f) The comment on Bangla consent form has been incorporated to reflect the English consent form.
- g) Provision of obtaining signature or thump impression of the subject (in stead of signature of thump impression of guardian) has been made in the Bangla consent form.
- h) Ref # 64 as mentioned in page 14 is correct
- i) We have included history of chronic blood loss as a excluding criteria in the protocol in page 16, section 2.4.

*The p 9 has incorporated all the comments made in the last meeting and addressed these issues appropriately. The protocol may now be approved for ethical clearance. See page 1 ([name]) Bsmmm*

A Revised Version of the protocol incorporating the comments is submitted herewith for your kind approval please.

INTERNATIONAL CENTRE FOR DIARRHOEAL DISEASE RESEARCH, BANGLADESH  
Mail : ICDDR,B, [name]  
[contact], [name]  

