*Helicobacter pylori* (Hp) is a major gastrointestinal pathogen that causes gastritis and low gastric acid production. Gastric acid is one of the most important luminal factors necessary for optimal non-haeme iron (Fe) absorption. Thus, low gastric acid is a risk factor for iron deficiency anemia (IDA), which affects millions of people, primarily infants and women in the reproductive age. We hypothesize that poor bioavailability of iron in these countries might be related to low gastric acid output resulting from Hp infection. The frequency of low gastric acid secretor and IDA in such population is not known. We, therefore, propose to investigate the frequency of *H. pylori*-associated low gastric acid secretor (hypochlorhydria) and to evaluate its role in causing IDA in women. One hundred sixty women in the reproductive age, living in Nandipara, a peri-urban community of Dhaka city will be studied to ascertain the frequency of *H. pylori*-associated low acid output and IDA. To investigate the role of Hp in causing hypochlorhydria and IDA, an intervention study is also planned. Four groups (25 in each group) of Hp-infected women with IDA and hypochlorhydria, and another group (fifth group) of 25 women with normochlorhydria will be studied. Hp infected women with IDA and hypochlorhydria will be assigned to one of the four interventions: (i) anti-Hp therapy (triple-therapy with clarithromycin, amoxicillin and omeprazole), (ii) anti-Hp triple therapy plus iron (ferrous fumarate), (iii) iron therapy alone, or (iv) placebo. The fifth group of women with Hp infection and IDA but without hypochlorhydria will be treated with anti-Hp therapy.

Urea breath test will be used for identification of *H. pylori* infection. Iron status will be determined by analyzing hemoglobin, serum ferritin, and circulating transferrin receptor. Electrical Impedance Tomography (EIT) will be used to assess basal and pentagastrin-stimulated gastric acid outputs. Urea breath test, iron status, and EIT will be repeated at the end of intervention, and at 3 and 6 months from the time of initiation of intervention therapy.

This study is expected to provide useful, new information on the role of *H. pylori* infection and hypochlorhydria in the etiology of IDA. The findings of this study, therefore, are likely to influence the design of iron fortification strategies/programmes for reducing the burden and consequences of IDA in the developing countries.

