## 2. Part 2: Testing of the second objective

### Randomized, double-blind, placebo-controlled, community trial

#### 2.1 Methods

To determine if there is a causal relationship of IDA with Hp infection, or if Hp infection has any relationship with IDA, an intervention study will be conducted on 100 Hp-infected women with hypochlorhydria and IDA. They will be randomized in equal numbers to receive either of the following four interventions:

- (i) Anti Hp therapy: A combination of 500mg clarithromycin twice daily + 500mg amoxicillin twice daily + 40 mg omeprazole once daily for 14 days
- (ii) Anti Hp therapy plus iron: The above + ferrous fumarate containing 60-mg elemental iron each day for 60 days
- (iii) Iron alone: Ferrous fumarate containing 60-mg elemental iron each day for 60 days
- (iv) Placebo: Starch powder

**Fifth group:** There will be a fifth group of 25 women with Hp infection but without hypochlorhydria. This group is required to observe the influence of hypochlorhydria *per se* on IDA. This group will also be treated with Anti-Hp therapy plus iron.

The therapies will be provided in gelatin capsules and will be fed daily in morning and at the evening. The women in the placebo group will receive same amount of starch powder in identical capsules for 60 days. To keep the study blind, all therapies will be kept in identical container and will be fed by a health worker who will remain unaware of the nature of the study and the contents inside the bottles.

The women will be followed for six months after the end of intervention. Hb, SF, and sTfR will be determined at the end of intervention and also, 3 and 6 months after the intervention. Urea breath test will also be performed at the same time. EIT will be repeated 6 months after intervention. The women in the placebo groups will be given anti-Hp therapy plus iron as indicated above at the end of study period of 6 months. Similarly the group (iii) women will also provided anti-Hp therapy at the end of the study. The dose of iron conforms to that used in Bangladesh ( Kolsteren et al 1999).

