### 2.3 Sample size

The sample size is determined with the assumptions that anaemia will be corrected in 95% women with Anti-Hp therapy plus iron-therapy, while iron therapy alone will correct anaemia in 60% of the women. Thus, the worthwhile difference (D) in correction of anemia will be:

$$D = 95 - 60 = 35\%$$

At 5% level of significance (type I error of 5%) with 80% power (type II error of 20%), and to detect a 35% difference in the outcome (correction of anaemia), the sample size has been estimated as follows:

$$n = 2 P(1-P) * (Z_{\alpha/2} + Z_{\beta})^2 / D^2$$

Where:  $P = (P_1 + P_2) / 2 = (95 + 60) / 2 = 77.5 \%$   
(  $P_1$  is 95% and  $P_2$  is 60% )

$$\begin{aligned} n &= 2 * 0.775 (1-0.775) * (1.96 + 0.86)^2 / (0.35)^2 \\ &= 1.55 * 0.225 * (2.82)^2 / 0.1225 \\ &= 0.34875 * 7.95 / 0.1225 \\ &= 22.6 \\ &\cong 23 \text{ subjects in each of the five groups} \end{aligned}$$

Based on previous study in the same community, we anticipate a drop out rate of approximately 10%. Therefore, the number of women to be enrolled is 25 in each group i.e.  $25 * 5 = 125$  women in total in 5 groups.

The reported prevalence of Hp infection is 80%. We estimate 60 % of infected population will be hypochlorhydric. of whom 70% will have IDA. We need to screen 298 ( $100 / 0.8 * 0.6 * 0.7$ ) women to identify 100 infected women (for four groups) with hypochlorhydria and iron deficiency anemia. As 160 women will be enrolled under the first part of the study we will require 138 ( $298 - 160 = 138$ ) additional women to be screened under the second part of the study.

We need a fifth group of 25 women with Hp infection but without hypochlorhydria. They will be selected from among these 260 women.

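### In the H. pylori trial, end-of-study treatment leaves out group (i), the only randomised arm that the text shown never gives iron

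*Protocol*

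**What the plan says.** The file holds two protocols; this point concerns the one on H. pylori and iron deficiency anaemia. Section 2.1 enrols 100 women who all have Hp infection, hypochlorhydria and IDA, and randomises them equally to (i) 14 days of anti-Hp therapy, (ii) the same plus 60 days of iron, (iii) iron alone, or (iv) placebo. Section 2.2 adds that women on a single active treatment also take a placebo for the one they do not get.

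Follow-up runs to six months after the intervention, with Hb, serum ferritin (SF) and transferrin receptor (sTfR) measured at its end. Section 2.1 then names two arms for treatment: "The women in the placebo groups will be given anti-Hp therapy plus iron as indicated above at the end of study period", and "Similarly the group (iii) women will also provided anti-Hp therapy at the end of the study". The reply to the Ethical Review Committee, item e, names the same two: "The placebo and the group (iii) with iron therapy alone will be provided anti-Hp therapy plus iron and Anti-hp therapy respectively". A note on that letter says the comments were dealt with and adds "The protocol may now be approved for ethical clearance".

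**The concern.** The two stated provisions follow one principle: once the data are in, a woman gets the component that her arm withheld. Placebo women lacked both components and get both. Group (iii) lacked anti-Hp therapy and gets it. Group (ii) lacked nothing. Group (i) lacked iron, and nothing is said of it.

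The study itself diagnoses these women as having IDA, withholds iron from them under blinding, and measures their iron status again at six months. The investigators will therefore know which of them still have IDA. Followed as written, section 2.1 gives those women no iron, while it gives iron to placebo women. What is at stake is participant care in women of reproductive age, for whom the protocol's own background section lists serious consequences of IDA.

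**Working it through.** Iron by randomised arm, from sections 2.1 and 2.2 and item e of the ethics reply:

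| Arm | IDA at entry | Iron during trial | Treatment stated for study end |
|---|---|---|---|
| (i) anti-Hp | yes | no (placebo) | none |
| (ii) anti-Hp + iron | yes | yes | none; has had both |
| (iii) iron | yes | yes | anti-Hp |
| (iv) placebo | yes | no | anti-Hp + iron |

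Group (i) is the only row with no iron in either column. Two other places might have filled it. The ethical assurance section makes a general promise of suitable medication, but names no arm, drug or time. The budget has a line for medicines including iron, but ties it to no arm.

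**Number affected.** The arm size comes from section 2.3: n = 2P(1−P)(1.96+0.86)²/D² with P = 0.775 and D = 0.35. This is 0.34875 × 7.95 / 0.1225 ≈ 22.6, so 23, as the plan states. The plan enrols 25 per arm, and of losses it says "we anticipate a drop out rate of approximately 10" per cent. Completers in group (i): 25 × 0.90 = 22.5, about 23.

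**Number still anaemic.** Section 2.3 assumes that "anaemia will be corrected in 95% women with Anti-Hp therapy plus iron-therapy", and 60% with iron alone. It gives nothing for anti-Hp therapy alone. Applying assumed correction rates c to the 22.5 completers:

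- c = 0: 22.5 × 1.00 = 22.5
- c = 60% (borrowed from iron alone): 22.5 × 0.40 = 9.0
- c = 95% (borrowed from the combination): 22.5 × 0.05 = 1.1

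These rates belong to other regimens. The range of about 1 to 23 spans nearly everything possible, so it is not an estimate.

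**Iron needed.** Ceiling for group (i): 25 × 60 = 1,500 daily doses, or 22.5 × 60 = 1,350 after drop-out. Section 2.1 already implies (25 + 25 + 25) × 60 = 4,500 for groups (ii), (iii) and the fifth group, plus 25 × 60 = 1,500 for placebo women at study end, 6,000 in all. The ceiling adds 1,500/6,000 = 25%.

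If the same rule covers every arm, the section 2.3 rates leave 25 × 0.05 = 1.25 women in group (ii) and 25 × 0.40 = 10 in group (iii) still anaemic before drop-out. That is 11.25 × 60 = 675 further doses, assuming those rates hold at six months. No rate is given for the fifth group. Placebo women already receive this course.

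**The case against.** The strongest reply is that this is an omission and not an error. Section 2.1 does not call its two provisions exhaustive and does not say that anyone will be refused iron. The consent forms, where post-study care is often described, are not among the pages available. The women would not be abandoned either: the institution has run a weekly clinic in this community since 1985, women with Hb below 8 g/dL are excluded at entry, and the ethical assurance is general enough to include group (i). The ethics committee had also looked at end-of-study treatment.

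Much of this stands as a limit on the claim. A reader might infer that the plan denies iron to group (i). The documents do not say so, and a rule on the missing pages cannot be excluded. Still, an explicit list of arms that leaves one out is what field staff would follow. The clinic is for minor illnesses and carries no commitment to iron. Neither the ethics reply nor the note on it mentions group (i), so they do not show that the omission was considered.

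It may also be said that anti-Hp therapy could itself correct the anaemia. That is part of what the trial tests and cannot be presumed when planning care.

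A further objection is that persistent IDA is not confined to group (i). That is right: on the plan's own 60%, about 10 of 25 women in group (iii) would remain anaemic and then get anti-Hp therapy with no further iron stated. A rule for group (i) alone would also separate (i) from (ii), which treating (iii) and (iv) does not do. Both points shape the fix.

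**Conclusion.** The gap is real on the text available and worth correcting. Group (i) is the only randomised arm, all of them with IDA at entry, that is given no iron during or after the trial. Up to about 23 completers of 25 are exposed to the gap. The number who would actually leave with untreated IDA is unknown.

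Two stronger readings are not supported. The first is that the trial's results suffer: the omitted iron would follow the last measurement, so outcomes, sample size and the powered comparison of (ii) with (iii) are untouched. The second is that the fifth group shares the gap and doubles the count to 50. That rests on the Project Summary, which says "The fifth group of women with Hp infection and IDA but without hypochlorhydria will be treated with anti-Hp therapy". Section 2.1, the detailed methods text, says "This group will also be treated with Anti-Hp therapy plus iron", and on that text the group has had iron. The mismatch between the two places is a separate point.

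The conclusion assumes that no rule for group (i) stands on the pages not available.

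**What to change.** Add to section 2.1, after the sentence on group (iii): any woman, whatever her arm, who at the final six-month visit has Hb below 12 g/dL together with low SF or raised sTfR (the cut-offs of section 1.1.4.2) is offered ferrous fumarate, 60 mg elemental iron daily for 60 days, after her final outcome measurements and in addition to the treatments already listed. Placebo women already receive this course and need no second one. Notify the ethics committee of the change.

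The rule turns on blood results and not on allocation, so it covers group (i) without separating (i) from (ii). It uses only the three tests that section 2.1 schedules at six months. The full IDA definition can also call on transferrin saturation, which section 2.1 does not schedule at that visit. The rule is therefore slightly broader than the definition. Section 1.1.4.1 notes that sTfR also rises in haemolytic anaemia, so the study physician should look at any woman who qualifies on sTfR alone.

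The cost is one paragraph and a letter, at most 1,500 daily doses for group (i), the doses for persistent cases in other arms, and one further contact to hand over the iron once results are back. No analysis changes.

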#### 2.2 Randomization

An experienced person not related in any way with the study will prepare a master randomization chart. A permuted block randomization with variable block length will be used. Box containing anti-Hp therapy, iron therapy, or placebo will be identical in appearance and will be arranged in sequence that corresponds to the randomization chart which will be sequentially numbered. The serial number of the box will correspond to the random number of women enrolled in the study. As one group of women would receive anti-Hp therapy and Fe therapy

Principal Investigator (Last, first, middle): [name]

simultaneously, there will be two boxes (boxes A and B) for each group of women to make the study double-blind. For women belonging to anti-Hp plus iron therapy, one box will contain anti-Hp therapy and the other box will contain Fe therapy. For women in the iron therapy or anti-Hp therapy groups alone, one of the boxes will contain active drug and the other will contain placebo for the other therapy. As the duration of therapy of anti-Hp therapy is 14 days, the women belonging to this group will be provided placebo capsules for the rest 44 days to maintain the double-blind nature of the study.

### 2.3 Sample size

The sample size is determined with the assumptions that anaemia will be corrected in 95% women with Anti-Hp therapy plus iron-therapy, while iron therapy alone will correct anaemia in 60% of the women. Thus, the worthwhile difference (D) in correction of anemia will be:

$$D = 95 - 60 = 35\%$$

At 5% level of significance (type I error of 5%) with 80% power (type II error of 20%), and to detect a 35% difference in the outcome (correction of anaemia), the sample size has been estimated as follows:

$$n = 2 P(1-P) * (Z_{\alpha/2} + Z_{\beta})^2 / D^2$$

Where:  $P = (P_1 + P_2) / 2 = (95 + 60) / 2 = 77.5 \%$   
(  $P_1$  is 95% and  $P_2$  is 60% )

$$\begin{aligned} n &= 2 * 0.775 (1-0.775) * (1.96 + 0.86)^2 / (0.35)^2 \\ &= 1.55 * 0.225 * (2.82)^2 / 0.1225 \\ &= 0.34875 * 7.95 / 0.1225 \\ &= 22.6 \\ &\cong 23 \text{ subjects in each of the five groups} \end{aligned}$$

Based on previous study in the same community, we anticipate a drop out rate of approximately 10%. Therefore, the number of women to be enrolled is 25 in each group i.e.  $25 * 5 = 125$  women in total in 5 groups.

The reported prevalence of Hp infection is 80%. We estimate 60 % of infected population will be hypochlorhydric. of whom 70% will have IDA. We need to screen 298 ( $100 / 0.8 * 0.6 * 0.7$ ) women to identify 100 infected women (for four groups) with hypochlorhydria and iron deficiency anemia. As 160 women will be enrolled under the first part of the study we will require 138 ( $298 - 160 = 138$ ) additional women to be screened under the second part of the study.

We need a fifth group of 25 women with Hp infection but without hypochlorhydria. They will be selected from among these 260 women.

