## Research Design and Methods

---

Describe in detail the methods and procedures that will be used to accomplish the objectives and specific aims of the project. Discuss the alternative methods that are available and justify the use of the method proposed in the study. Justify the scientific validity of the methodological approach (biomedical, social, or environmental) as an investigation tool to achieve the specific aims. Discuss the limitations and difficulties of the proposed procedures and sufficiently justify the use of them. Discuss the ethical issues related to biomedical and social research for employing special procedures, such as invasive procedures in sick children, use of isotopes or any other hazardous materials, or social questionnaires relating to individual privacy. Point out safety procedures to be observed for protection of individuals during any situations or materials that may be injurious to human health. The methodology section should be sufficiently descriptive to allow the reviewers to make valid and unambiguous assessment of the project. **(DO NOT EXCEED TEN PAGES, USE CONTINUATION SHEETS).**

---

This study has two parts to address its two objectives, which complement each other, and will be done, in sequence to test our hypothesis.

1. **First part:** To determine prevalence of *H. pylori* infection, low gastric acid secretion and IDA in Bangladeshi women in the reproductive age living in a peri-urban community of Dhaka City.
2. **Second part:** To conduct a randomized, double-blind, placebo-controlled field trial in the same population to determine if *H. pylori* infection is causally linked to iron deficiency anemia in this population.

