### 1. Part 1: First Objective of the Study

**To determine the prevalence of *H. pylori* infection, low gastric acid secretion, and iron deficiency anaemia in Bangladeshi women in the reproductive age living in a peri-urban slum of Dhaka city.**

One hundred sixty (160) adult women aged, 20-40 years, living in Nandipara, a peri-urban community of Dhaka city will be screened for *H. pylori* infection using the  $^{13}\text{C}$ -urea breath test. Their gastric acid secretion will be assessed by the non-invasive, Electrical Impedance Tomography ([name] et al. 1997); and their body iron status will be determined. All subjects will be fully informed about the aims of the study and the procedures to be followed, and written informed consent will be obtained before their enrollment in the study.

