### 1.1.5 Sample Size

#### *Prevalence of HP-linked IDA and Hypochlorhydria*

The reported prevalence rate of *Helicobacter pylori* infection in the community is 80%. We assume 60% of the Hp-infected women will have hypochlorhydria and 70% of the Hp-infected hypochlorhydric women will have iron deficiency anaemia. However, we like to have an estimate of the prevalence of Hp infection plus hypochlorhydria plus iron deficiency anaemia to be corrected within  $\pm 5.0\%$  with 95% confidence

The required sample size will be:

$$\frac{\epsilon}{\sqrt{PQ/n}} = Z_{\alpha}$$

Where  $\epsilon$  = allowable error  
P = estimated prevalence  
Q = 1-P  
n = the required sample size  
 $Z_{\alpha}$  = value of the normal variation for (1- $\alpha$ )% confidence

Assuming:

$$\epsilon = 7.5\%$$

$$P = 0.8 * 0.6 * 0.7 \\ \cong 34\%$$

$$Q = 1-P = 66\%$$

$$\text{and } Z_{\alpha} = 1.96 \text{ (95\% confidence)}$$

The required sample size of Hp infected women with hypochlorhydria and IDA:

$$\frac{\epsilon}{\sqrt{PQ/n}} = Z_{\alpha}$$

$$\frac{0.075}{\sqrt{0.34 * 0.66/n}} = 1.96$$

Therefore  $n = 1.96^2 * 0.34 * 0.66 / 0.075^2$   
= 154 women. However, we will take 160 sample.

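### The joint prevalence in the H. pylori study is sized and described on 160 women, although 138 more women from the same population are screened for the same joint status

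*Protocol*

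**What the plan says.** All references are to the H. pylori protocol, including the letter to the Ethical Review Committee of October 18, 1999.

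- **Part 1, the prevalence survey.** The first objective names its sample: "One hundred sixty (160) adult women aged, 20-40 years, living in Nandipara". Section 1.1.5 calculates 154 and rounds up: "However, we will take 160 sample". The committee letter gives the same number and purpose: "We will initially study 160 women to determine the prevalence of" infection, low acid secretion and anaemia. In the Project Summary the 160 women "will be studied to ascertain the frequency of" Hp-associated low acid output and IDA.
- **Part 2, the additional screening.** Section 2.3 needs 298 women in all to yield 100 for the four randomised groups, and continues: "As 160 women will be enrolled under the first part of the study we will require 138". The letter agrees: "For the Part 2 of the study, we will screen another 138 women".
- **Same source.** Research Design and Methods gives the second part as: "To conduct a randomized, double-blind, placebo-controlled field trial in the same population".
- **Comparison of IDA by acid status.** Data Analysis defines a chi-square test in Hp-infected women, split at an EIT area under the curve of 300. It gives no sample size and no restriction to Part 1.
- **Exclusions.** Section 2.4 lists them under Part 2. Whether they also govern the Part 1 survey is not stated.

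**The concern.** A woman screened for Part 2 must be classified on Hp infection, acid secretion and iron status before she can be called eligible. Her joint status is exactly the quantity that Part 1 estimates. This is true even if the tests are done stepwise, because a negative result on any one of them already makes her a non-case. The 138 women are 138/298 = 46% of all women screened.

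Prevalence is specific aim 1, and its precision is the only basis given for the 160. Section 1.1.5 says that the estimate should be within 5.0% with 95% confidence, but then calculates with 7.5%. With 160 women the first figure is missed by a wide margin. The further screening is already planned, so leaving it out of the estimate would give up precision that the study has paid for.

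The timing matters as well. Whether the two batches can be combined depends on how the 138 are recruited and on when exclusions are applied. Those are field procedures, and later analysis cannot fully repair them if they differ.

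**Working it through.** **Inputs.** Hp prevalence 80%, hypochlorhydria among infected women 60%, IDA among those 70% (sections 1.1.5 and 2.3). P is rounded to 0.34, the allowable error used is 0.075, and z = 1.96 (section 1.1.5). The survey has 160 women and the trial needs 100 eligible women.

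**1. The protocol's own figures.**
- Joint prevalence: 0.8 × 0.6 × 0.7 = 0.336, rounded to 0.34.
- Part 1: n = z²P(1 − P)/e² = 1.96² × 0.34 × 0.66 / 0.075² = 153.3, so 154, taken as 160. Reproduced.
- Screening total: 100/(0.8 × 0.6 × 0.7) = 100/0.336 = 297.6, so 298, and 298 − 160 = 138. Reproduced. The printed expression lacks brackets and read literally gives 52.5, but 298 is clearly what was meant.

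**2. Precision of the joint prevalence.** Half-width = 1.96 × √(P(1 − P)/n), with P = 0.34.

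| Women in the estimate | Calculation | 95% half-width |
|---|---|---|
| 160 | 1.96 × √(0.2244/160) | 7.3 points |
| 298 | 1.96 × √(0.2244/298) | 5.4 points |
| 260 (the other total mentioned in section 2.3) | 1.96 × √(0.2244/260) | 5.8 points |

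Using 0.336 in place of 0.34 leaves all but the last row unchanged to one decimal; that row becomes 5.7. The ratio √(160/298) = 0.73 means an interval about 27% narrower.

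**3. Against the stated aim.** A half-width of 5.0 points needs 1.96² × 0.34 × 0.66 / 0.05² = 344.8, so 345 women. The 298 come close to that and the 160 do not.

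**4. Finite population.** The Facilities section puts the community at about 750 women of reproductive age. Multiplying by √((750 − n)/749) would give 6.5 and 4.2 points (at P = 0.336). I do not rely on these, because Part 1 samples ages 20–40 and the size of that group is not given.

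**5. Stopping rule.** If screening ends when the 100th eligible woman is found, the total N is random and the simple proportion 100/N is slightly biased upwards. The inverse-sampling estimate is (100 − 1)/(N − 1). At N = 298 it is 99/297 = 33.3%, against 100/298 = 33.6%. The correction is small beside a half-width of 5.4 points.

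**The case against.** **Silence is not exclusion.** No sentence says that results from the 138 will be left out, and analysis sets can be defined in a statistical analysis plan that is not at hand. This stands in part. A reader might infer that 46% of the data are to be discarded, and the document does not support that. It does, however, repeatedly assign and size the prevalence estimate on 160 women, so the point about prevalence rests on what is written. The recruitment and exclusion rule that pooling needs also has to be settled before fieldwork.

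**The comparison of IDA by acid status.** A reader might also infer that this comparison is fixed at the first 160 and is therefore underpowered. That does not hold. Data Analysis defines it for Hp-infected women by acid group and would admit every infected woman screened. Any power figure would also need an IDA rate in normal-acid women, which the protocol does not give. Nor is it certain that the 138 can all enter. If blood tests come first and the two-hour EIT with pentagastrin is omitted in women without IDA, acid status would be missing for them.

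**Identical testing is implied, not stated.** Section 2.3 gives no test procedure or order for Part 2. This is true, but the protocol describes only one method each for infection, acid and iron status. Section 2.3 also applies one set of rates to the whole 298, so it already treats the batches as alike.

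**Keeping the survey at a fixed n is defensible.** The section 2.4 exclusions include Hb below 8 g/dL, hookworm, occult blood and chronic blood loss. Applied to the 138 only, they would select on variables related to IDA, and pooling would bias the prevalence. This stands and makes the recommendation conditional. It is also true that 160 satisfies the 7.5% actually used in the calculation; the conflict between 5.0% and 7.5% is a separate matter.

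**Conclusion.** The point holds for the joint prevalence. The protocol plans it on 160 women while screening 138 more from the same population for the same joint status, and it does not say whether they count. Using all 298 would reduce the 95% half-width from about 7.3 to 5.4 percentage points at P = 0.34, close to the 5.0% that section 1.1.5 states.

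This rests on three assumptions: that the 298 is carried out as planned, that the planning rates are roughly right, and that both batches are sampled and excluded under one rule. The gain is confined to the joint prevalence. If Part 2 tests are stepwise, the separate prevalences of hypochlorhydria or IDA can use only women who had the relevant test.

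This is a worthwhile and cheap gain in precision. It does not invalidate any planned result. For IDA by acid status the only gap is an unstated denominator.

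**What to change.** 1. In sections 1.1.5 and 2.3 and in Data Analysis, state that the joint prevalence of Hp infection, hypochlorhydria and IDA is estimated from all 298 screened women.
2. State that the additional 138 are sampled in the same way as the 160, including the age range, and under the same eligibility and exclusion rule. Say explicitly whether section 2.4 applies to the Part 1 survey. If its exclusions are applied to the 138 only, the two batches are not to be pooled and the estimate stays with the 160.
3. Say whether screening ends at 298 women or at the 100th eligible woman. In the second case, specify the inverse-sampling estimate.
4. For the chi-square test of IDA by acid status, add that all screened Hp-infected women with both acid and iron results are included. At the planning rate of 80%, infected women number about 0.8 × 160 = 128 in Part 1 and 0.8 × 298 = 238 overall; how many of the latter have both results depends on the order of tests.
5. Reconcile the 260 women in the last sentence of section 2.3 with the 298.

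**Cost.** Mostly wording, with no additional women. The one real demand is a common sampling and exclusion rule for both batches, which has to be observed in the field.
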